### 3.4 Neuropsychological Assessments

In order to investigate the psychological (e.g., affect, stress/well-being) correlates of brain dopamine D2BP, participants will complete various questionnaires and tasks during the inpatient

phase. Assessments conducted in advance of/during screening visit (as noted) mainly used to confirm eligibility criteria.

1. **National Adult Reading Test - Revised (NART-R) [17]:** The NART-R is a commonly used measure of intelligence for native English-speaking adults. The test comprises 50 written words in American English, and all words have irregular spellings to examine the subject's vocabulary and not their ability to apply regular pronunciation rules. NART-R scores can be used as a proxy for intelligence as measured by the Wechsler Adult Intelligence Scale. This test takes approximately 5 minutes. Completed during screening visit. Participants are eligible if their estimated IQ is greater than or equal to 70 points. If excluded on the basis of IQ estimation from the NART, participants will be informed that they did not meet study inclusion criteria on the basis of their "reading test results".
2. **Eating Disorder Examination Questionnaire (EDE-Q) [14]:** The EDE is a self-report questionnaire derived from the Eating Disorder Examination clinical interview (EDE), designed for the assessment of anorexia nervosa, bulimia nervosa, and binge-eating disorder, as defined by the DSM-5. The questionnaire is a 28-item measure with questions pertaining to frequency of behaviors, feelings, and attitudes occurring in the past 28-days. Completion of the survey yields four subscale scores: Restraint, Shape Concern, Weight Concern, and Eating Concern, as well as a Global score incorporating all four subscales. As we aim to exclude individuals with evidence of eating disorders, subjects who receive a clinically significant score in any section will be excluded from remaining portions of the study. The questionnaire will take approximately 15 minutes. Completed during screening visit.
3. **DSM-5 Self-Rated Level 1 Cross-Cutting Symptom Measure [22]:** This questionnaire is delivered during the screening visit and assesses mental health domains that are important across psychiatric diagnoses. It consists of 23 questions that assess 13 psychiatric domains, including:  
Depression  
Anger  
Mania  
Anxiety  
Somatic symptoms  
Suicidal ideation  
Psychosis  
Sleep problems  
Memory  
Repetitive thoughts and behaviors  
Dissociation  
Personality functioning  
Substance use

Each item asks about how much (or how often) the individual has been bothered by the specific symptom during the past 2 weeks. Each item on the measure is rated on a 5-point scale. Critical items, and follow-up measures are provided for each disorder. The

questionnaire will be administered in REDCap and scored in real time. If the subject scores raise concerns about one or more disorders, the results will be discussed with a medically qualified team member who will follow up with the participant for further inquiry. Participants will be notified of any clinically meaningful to provide/discuss with their primary care physician as desired. Completed during screening visit.

4. **Positive and Negative Affect Schedule - Expanded Form (PANAS-X) [23]:** The PANAS is a widely used measure comprising 60-items assessing general states of positive and negative affect using 5-point scales (1 = very slightly/not at all, 5 = extremely). The PANAS-X measures 11 specific affects: Fear, Sadness, Guilt, Hostility, Shyness, Fatigue, Surprise, Joviality, Self-Assurance, Attentiveness, and Serenity. To assess momentary affect, participants will rate how they feel “right now at the present moment”. The PANAS has high internal consistency, good convergent, discriminant, and construct validity, and is one of the most commonly used mood measures [24]. Completed during inpatient visit (phase B).
5. **UPPS-P Impulsive Behavior Scale [25]:** The UPPS-P is a 59-item self-report questionnaire used to assess impulsivity based on five subscales: urgency, premeditation, perseverance, sensation seeking, and positive urgency. Each item is rated using a 4-point Likert scale, ranging from 1 to 4: 1 (Agree Strongly), 2 (Agree Some), 3 (Disagree Some), 4 (Disagree Strongly). The questionnaire takes approximately 20 minutes to complete. Completed during inpatient visit (phase B).
6. **Pittsburg Sleep Quality Index (PSQI) [61]:** The PSQI is a 19-item, self-rated questionnaire which assesses sleep quality, latency, duration, habitual sleep efficiency and related disturbances (e.g., use of sleeping medication and daytime sleepiness) over a 1-month time interval. Scoring reliably distinguishes good and poor sleepers. The questionnaire takes approximately 10 minutes to complete. Completed during inpatient visit (phase B).
7. **Depression, Anxiety, Stress Scales (DASS-21) [26]:** The DASS-21 is a set of three self-report scales designed to measure the negative emotional states of depression, anxiety and stress. Each of the three DASS21 scales contains 7 items per scale. Subjects are asked to use 4-point severity/frequency scales to rate the extent to which they have experienced each state over the past week. Scores for Depression, Anxiety and Stress are calculated by summing the scores for the relevant items. As the scales of the DASS have been shown to have high internal consistency and to yield meaningful discriminations in a variety of settings, the scales should meet the needs of both researchers and clinicians who wish to measure current state or change in state over time (e.g., in the course of treatment) on the three dimensions of depression, anxiety and stress. Completed during inpatient visit (phase B). Although the results of this test will not be returned to the participant, scores are subject to “real time” monitoring to facilitate alerting research team that additional follow-up is needed if scores exceed pre-defined thresholds (see section 5.1).

8. **Beck Depression Inventory (BDI-II) [27]:** The BDI-II is a 21-item self-report measure that has been used extensively in both community and clinical settings to assess depressive symptoms (e.g., changes in sleeping habits, appetite or feelings of hopelessness). Responses are recorded on a 4-point Likert scale, where greater total scores indicate increases in depressive symptoms. This questionnaire lasts 5 minutes. Completed during inpatient visit (phase B). Although the results of this test will not be returned to the participant, scores are subject to “real time” monitoring to facilitate alerting research team that additional follow-up is needed if scores exceed pre-defined thresholds (see section 5.1).
9. **State and Trait Anxiety Inventory (STAI) [28]:** This self-report questionnaire consists of 60 items that assess respondents’ experience of transient (state) and chronic (trait) anxiety and arousal. Subjects will complete these items using a 4-point Likert scale. This measure is completed in approximately 5 – 10 minutes. Completed during inpatient visit (phase B).
10. **Satisfaction with Life Scale (SWLS) [29]:** Satisfaction with Life Scale includes 5 items that assess general (e.g., my life is going well) aspects of subjective well-being. Completed during inpatient visit (phase B).
11. **Cohen Perceived Stress Scale (PSS) [30]:** This 10-item self-report measure for adults (ages 18 and above) assesses how unpredictable, uncontrollable, and overloading respondents find their lives. Each item is rated on a 5-point scale from 0 to 4, and greater total scores indicated increased perceived stress. Completed during inpatient visit (phase B).
12. **MacArthur Socioeconomic Status (SES) Questionnaire [31]:** The MacArthur SES questionnaire is a widely used self-assessment questionnaire. It begins with subjective social status questions, followed by questions assessing educational attainment, occupational status, income and assets. Completed during inpatient visit (phase B).
13. **Three-Factor Eating Questionnaire (TFEQ) [32]:** The three-factor eating questionnaire (TFEQ) is a self-assessment questionnaire developed to measure dietary restraint, disinhibition and hunger. The questionnaire contains 36 items with a yes/no response, 14 items with a 1-4 response scale and 1 item with a 1-5 response scale. Completed during inpatient visit (phase B).
14. **Binge Eating Scale (BES) [33]:** This 16-item self-report measure was developed to assess the presence of binge-eating pathology in obese individuals. Behavioral (e.g., quantity of food, loss of control) and cognitive (e.g., guilt, shame) features of binge eating are determined, where each question has 3 – 4 possible response items. Scores range from 0 – 48, and higher scores are indicative of greater severity. Completed during inpatient visit (phase B).
15. **Yale Food Addiction Scale 2.0 (YFAS 2.0.) [34]:** The YFAS 2.0 is a self-report questionnaire designed to assess the presence and severity of addictive-like eating. Items

were adopted from diagnostic criteria for substance use disorders, and respondents are provided with a binary ‘diagnosis’ of food addiction, as well as severity ratings (none, mild, moderate, severe). Completed during inpatient visit (phase B).

- 16. Barrett’s Impulsiveness Scale (BIS) [35]:** The BIS is a measure of trait impulsivity that has been validated in both community and patient populations, particularly among those with externalizing disorders. The 30-item questionnaire can be reduced to six first-order factors: attention, motor, self-control, cognitive complexity, perseverance, and cognitive instability. Completed during inpatient visit (phase B).
- 17. Monetary Choice Questionnaire (MCQ) [36]:** This 27-item self-report assessment requires respondents to indicate a preference for monetary rewards, which can either be delivered “Now” or “Later.” Consistent evidence has shown that humans value rewards less as time to delivery increases, a phenomenon known as “delay discounting,” and steep discounting of rewards has been associated with impulsiveness. Degree of discounting will be calculated using either the hyperbolic  $k$  parameter or an area-under-the-curve analysis. Completed during inpatient visit (phase B).
- 18. Fagerstrom Nicotine Dependence Test (FNDT) [15]:** This is a standard self-report measurement provides an ordinal measurement of an individual’s addiction to nicotine as it is related to cigarette smoking. Binary (yes/no) items are coded as 0 or 1, and multiple-choice items are score from 0 – 3, where higher total scores indicate greater nicotine dependence. Completed during screening visit.
- 19. Liking Survey:** Subjects will complete a validated, 100-item liking survey comprised of foods, beverages, physical activities, sedentary activities, pleasant experiences, and unpleasant experiences [37, 38]. The survey will take about 5–10 min to complete. Subjects will be oriented to the liking scale with examples of activities that are generally considered highly likeable (winning the lottery, succeeding), neutral (doing a routine chore), and highly dislikeable (getting a paper cut, running out of money). The bidirectional, horizontal scale ranged from “strongest disliking of any kind” (-100) to neutral (0) and “strongest liking of any kind” (+100) labeled with five faces (Pallister et, 2015) Each item has a word label and a picture. The items are grouped into eighteen nutritional, sensory, or activity groups: alcohol, sweet foods, fruits, vegetables, low-fat protein, high-fat protein, sweet drinks, fats, carbo- hydrates, whole grains, salty, bitter, sour, spicy/flavorful, physical activities, pleasant experiences, and unpleasant experiences [39]. Completed during inpatient visit (phase B).
- 20. Edinburgh Handedness Inventory [40, 41]:** Subjects will complete a short (~1 minute) survey in order to objectively determine whether one is left or right handed. Handedness will be used to better understand results of structural/functional brain imaging analyses. Completed during inpatient visit (phase B).
- 21. Apathy Motivation Index (AMI) [62]:** Subjects will complete a short questionnaire (<10 minutes) in order to assess general motivation characterized by action initiation and goal

directed behavior. The 18-item questionnaire will be administered in REDCap and will take less than 10 minutes to complete (phase B).

- 22. Big 5 Personality Test [e.g. 63]** To assess participants degree of extraversion, neuroticism, agreeableness, conscientiousness and openness to experience, participants will read statements querying their perception themselves in a variety of situations and asked to indicate the strength of agreement with each statement, choosing the best response on the scale ranging from strong disagreement (1) to strong agreement (7). The questionnaire will be administered via REDCap and will take less than 30 minutes to complete (phase B).
- 23. Self reported Habit Index [64]** is a 12-item scale which assesses more behavioral automaticity than cue-dependency. Participants will complete this short (<10 minute) survey on REDCap. (phase B).
- 24. Creature of Habit Scale [65]** is a 27-item questionnaire collected in REDCap that reflects variations in individuals' tendencies towards responding in a habitual manner in everyday life, particularly with respect to routine and automatic (disinhibited) responses to food (phase B).
- 25. Reward based eating drive scale (RED-13) [66]** questionnaire administered in REDCap to assess reward related eating. The RED-13 is a 13 item questionnaire designed to capture more variance at lower levels of reward related eating, so it may be more sensitive to subtle changes in the reward related eating construct at the milder end of this continuum (phase B).

### **3.5 Computer and Laboratory Tasks**

In order to investigate the psychological correlates of brain dopamine D2BP, participants will complete the following survey and computer tasks over the course of their inpatient visit.

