### **2.3.3 INPATIENT NEUROIMAGING SCHEDULE (PHASE B)**

Based on the screening visit (Phase A), consenting volunteers will be scheduled for study Phase B (inpatient visit to the MCRU at the NIH Clinical Center), preceded by up to 5 days of dietary stabilization as described above. This phase (B) of the study will occur as up to 6 contiguous inpatient days (depending on facility availability). To control for the impact of gonadal hormones on food intake, every effort will be made so that female subjects of reproductive potential will be admitted during the follicular phase of their menstrual cycle.

Following admission for Phase B, volunteers will undergo metabolic measurements consisting of: body weight and height; measurement of body composition (e.g., dual energy x-ray absorptiometry (DEXA), air-displacement plethysmography (BodPod)) and they will complete a battery of self-report questionnaires and computer tasks related to mood, stress, thoughts about food and eating, and self-control. Female subjects of reproductive potential will also complete a urine pregnancy test on Day 1 of the inpatient visit and interviewed about the possibility of pregnancy. Positive test results will preclude subjects from further participation. The purpose of these measurements is to facilitate examination of exploratory aims by providing a comprehensive assessment of whole-body composition in the subjects, as well as measures of cognitive processes that subserve typical food intake and feeding behaviors. The baseline measurements will then be compared with similar measurements during the 1-year follow-up. Except where noted, subjects will be provided a standard breakfast, lunch and dinner (approximately 50% calories from carbohydrate, 35% from fat and 15% of calories from protein) along with coffee/tea or diet soda in accordance with their usual intake.

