### **3.2 MRI Data Acquisition**

MRI studies may be performed by both the Biomedical & Metabolic Imaging Branch (NIDDK) on a 3.0T Siemens Verio whole body instrument and/or the NMR Center on a GE 3T

scanner. A 70 cm tube resonator will be used for radio frequency transmission and detection. Padding will be used to minimize motion. Including clinical images to be read by radiology, MRI portion will take less than 120 minutes. The participant will be asked to provide a venous blood sample prior to MR imaging. Imaging may take place 3-5 hours after a standard meal, depending on facility availability.

We will be using the MRI for investigational research. This means that the way the MRI is generating the images may be different than what is normally done in a routine clinical scan. However, all studies done under this protocol will be performed within FDA safety guidelines. To collect images for research, we will use standard clinical coils (antennae). These are parts of the machine that help generate the image. Additionally, we will use clinical MR machines used within the FDA safety guidelines.

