#### **3.5.1 INTERNAL STATE VISUAL ANALOG SCALES**

*Hunger and satiety assessments.* At various points over their inpatient admission and outpatient follow-up visit, subjects will be asked to complete a survey to identify their perception of hunger (i.e., visual analog scale [VAS]) [42]. More specifically, the VAS survey will consist of four questions: 1) "How hungry do you feel right now?" 2) "How full do you feel right now?" 3) "How much do you want to eat right now?" and 4) "How much do you think you can eat right now?" Below each question on the survey there is a horizontal 100mm line with qualifying statements such as "Not at all"/"The least I can possibly" and "Extremely"/"The most I can possibly", anchoring the line on the extreme left and right side, respectively. In response to each question, subjects will be asked to digitally draw a vertical mark on the horizontal line to represent the magnitude of their response to the question. A value for each response is quantified by measuring the distance of their mark (in mm) relative to the left end of the line. Therefore, the values (or "scores") for each question range from 0 to 100.

*Intensity assessments.* In order to assess participants' interoceptive awareness of their GI sensations, participants will also be asked to rate the intensity of their overall sensations in their

stomach in relation to four specific stomach sensations: hunger, fullness, pain, and nausea. At various points over their inpatient admission and outpatient follow-up visit, a computerized VAS will be presented on a computer tablet, and participants will use a finger to slide a bar across the scale to indicate their subjective experience. The scales are anchored from 0 (*No Sensation*) to 100 (*Extremely Intense Sensation*).

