### **3.5.2 LIKING & WANTING**

Subjects will complete the Liking and Wanting computer assessment. The liking and wanting procedure comprises two tasks designed to assess (1) explicit liking and wanting, followed immediately by (2) implicit wanting for the same target food stimuli [43, 44]. The separate task elements will be integrated to fully randomize explicit and implicit trials. Experiment generator software (E-prime v2.0) is used to integrate the single stimulus trials for the liking task with the paired stimuli trials for the wanting task. Food stimuli presented in the procedure are selected from a database of photographic stimuli and sorted according to their fat content and taste properties into one of four separate categories: high-fat savory (HFSa); low-fat savory (LFSa); high-fat sweet (HFSw); and low-fat sweet (LFSw). Each category is represented by four different foods; hence a total of 16 different food stimuli will be presented in the procedure.

The aim of the explicit task is to obtain introspective hedonic measures for the same stimuli used in the implicit wanting task. Therefore, each food stimulus is assessed independently using visual analogue scales (VAS). The explicit computer task trials consist of 16 food stimuli presented one at a time and rated according to a 100-mm VAS anchored at each end by the statements “not at all” and “extremely”. Subjects will be prompted with the statements “How pleasant would it be to taste some of this food now?” and “How much do you want some of this food?” Responses on the software will be recorded online and mean ratings for each food category (HFSa, LFSa, etc.) are automatically computed.

Implicit wanting is measured by a behavioral “forced choice” methodology. In this task, a food stimulus from one of the four food categories is paired with one stimulus from the remaining categories to form a series of 96 trials in which the subjects will be given the standardized instruction to select the food they “most want to eat now”. In addition to recording the frequency of selections made in each category (with a possible range of 0–48), which may reveal a relative preference, reaction time (in milliseconds) of each choice is also measured. By covertly recording reaction time, subjects will be unaware of implicit changes in their behavior on the task, while remaining free to determine the direction of their choices.

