To evaluate subjects' ability to detect differences in the amounts of fat and sugar, subjects will sample without swallowing the five solutions differing in sugar concentration during one session and the five puddings that differed in fat during another. Subjects will rinse three times after tasting each sample. After each sample is tasted, they will be asked to rank them from least to most sweet or from least to most creamy, respectively. Subject responses will be scored from 0 to 2, following Stewart et al. [58]. A score of 2 indicated all correct (for example, 3.1, 6.9 and 15.6% wt/wt); a score of 1 indicated one was correct and the other two were adjacent to each other (for example, 3.1, 15.6 and 6.9% wt/wt); and a score of 0 indicated that all were incorrect (for example, 6.9, 15.6 and 3.1% wt/wt).

All taste samples will be kept chilled and brought to room temperature prior to testing. Testing will be performed after at least 2 hours of fasting and last approximately 1 hour.

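### Liking & Wanting and food delay discounting ask about eating now but have no fixed time since the last meal, which adds avoidable noise to their exploratory correlations with D2BP

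*Combined protocol and SAP*

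**What the plan says.** Section 3.5 introduces the computer tasks with one timing statement: "participants will complete the following survey and computer tasks over the course of their inpatient visit". Section 2.3.3 adds that, after admission, participants do a battery of "self-report questionnaires and computer tasks related to mood, stress, thoughts about food and eating, and self-control". Neither place gives a clock time, a time since the last meal or a fasting state.

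In section 3.5.2 the explicit liking prompt is "How pleasant would it be to taste some of this food now", and the forced-choice instruction is to pick the food they "most want to eat now". The explicit wanting prompt, "How much do you want some of this food", has no time reference. In section 3.5.3 the participant chooses between eating a pictured, well-liked food immediately and a sum of money; the section presents discounting as a possible index of impulsive decision-making.

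Hunger is rated under section 3.5.1: "At various points over their inpatient admission and outpatient follow-up visit, subjects will be asked to complete a survey to identify their perception of hunger". The stress and craving scales in section 2.3.3 belong to the PET sessions. Exploratory Aim 4 (section 1.3) relates task scores to D2BP, which is measured after an overnight fast. Section 4 gives no analysis of the task scores and no adjustment for hunger or time since eating.

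**The concern.** A question about what one would like to eat at this moment has a different answer before breakfast and after lunch. If participants answer it at different intervals after eating, part of the spread in scores reflects the meal schedule and not the person. Each participant contributes one baseline score to the correlation with D2BP, so this spread cannot be averaged out. Unless hunger is rated beside the task, or the time of last intake is kept, it cannot be reliably removed at analysis either.

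At stake is the usefulness of Aim 4 for generating hypotheses: real associations would look weaker than they are. The same gap affects change over a year. Section 2.3.5 repeats computer tasks at an outpatient visit, and section 2.3.3 says baseline measurements will be compared with similar ones at follow-up, but no matching prandial state is set.

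**Working it through.** **Reading the sections together**

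| Procedure | State set in the protocol |
|---|---|
| PET (2.3.3, 3.1.1) | Overnight fast |
| Resting energy expenditure (3.3.1) | 12-hour fast |
| Psychophysical taste test (3.6.2) | "Testing will be performed after at least 2 hours of fasting and last approximately 1 hour" |
| MRI (3.2) | "Imaging may take place 3-5 hours after a standard meal, depending on facility availability" |
| Liking & Wanting (3.5.2) | None |
| Delay discounting (3.5.3) | None |

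The first three are set conditions; the MRI statement is permissive. During the stay a participant passes through overnight fasts, standard meals (2.3.3), a 420 Cal milkshake (3.1.2) and an ad libitum lunch offering more than a day's energy requirement (3.6.3). As written, the two tasks may fall anywhere among these.

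**Illustration of size**

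The plan states no figure for the task scores, so there is none to reproduce. Inputs:

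- n = 39 (section 4).
- Two-sided 5% (section 4 gives 5% for the BMI test without stating sidedness).
- True correlation r = 0.45. This is an assumption, borrowed from the BMI–D2BP correlation in section 4 because none is given for task scores.
- h, the share of observed score variance due to momentary hunger unrelated to D2BP. This is an assumption, varied from 0 to 0.4.

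Formulas: observed r = r × √(1 − h); power = Φ(atanh(observed r) × √(n − 3) − 1.96), with √36 = 6.

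| h | Observed r | Power |
|---|---|---|
| 0 | 0.45 | 83% |
| 0.1 | 0.43 | 78% |
| 0.2 | 0.40 | 73% |
| 0.3 | 0.38 | 66% |
| 0.4 | 0.35 | 59% |

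For h = 0.2: 0.45 × √0.8 = 0.402; atanh(0.402) × 6 − 1.96 ≈ 0.60; Φ(0.60) ≈ 0.73.

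The 83% starting point is below the 89% that section 4 states for r = 0.45 with 39 subjects. The same formula gives 83% two-sided and 90% one-sided. On a one-sided basis the row for h = 0.2 becomes 82% and the row for h = 0.4 becomes 70%.

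The result depends on the assumed inputs. With a true r of 0.6 at n = 39, two-sided power goes from 99% (h = 0) to 95% (h = 0.2) and 86% (h = 0.4). With r = 0.45 and all of the maximum 60 participants in section 2.1 contributing, √57 = 7.55 and power goes from 95% to 90% and 78%. In the other direction, section 1.3 warns that some measures may be missing for some participants.

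**The case against.** The strongest reply is that this is a small operational matter in a hypothesis-generating aim, partly handled already. Inpatient meals have a standard composition, the hunger scale sits in the same section as the tasks and is repeated during the stay, and forced-choice counts are relative, so a general rise in appetite cannot lift every category together. All of that is fair and limits the size of the problem. None of it fixes the interval between eating and testing, and hunger could still change the mix of foods chosen. Figure 2 could not be read in the available copy, but its caption calls it an example schedule and no text ties these tasks to meals.

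Several stronger readings are tempting and not supported:

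- **Go/No-Go has the same fault.** Section 3.5.5 asks for button presses to target images and scores reaction time, hits and false alarms. It contains no wording about the present moment.
- **The protocol already sets a 3–5 hour standard that these tasks miss.** The MRI statement is optional and depends on facilities. The firmer comparators are the taste test, resting energy expenditure and PET.
- **Uneven timing creates a false correlation with D2BP.** That requires task timing to be related to D2BP, for example through BMI stratum or scan order. The documents do not show this, and scan order is to be randomised as far as scheduling allows.
- **Hunger must be a covariate.** If D2BP relates to food wanting partly through hunger, compulsory adjustment could remove the association being sought.

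**Conclusion.** The point holds for two tasks: Liking & Wanting (the liking prompt and the forced choice) and delay discounting. Followed as written, the plan lets time since eating vary freely between participants and does not ensure the information needed to account for it. This adds noise to Exploratory Aim 4 and to any one-year comparison of these tasks. No primary aim is touched, so this is a worthwhile improvement and not a serious flaw.

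A reader might take the fall from 83% to between 73% and 59% as the expected loss. It is not: both the hunger share and the true correlation are assumed, and section 4 claims no power for the exploratory aims. The conclusion rests on the task wording and the missing timing rule, not on those figures.

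**What to change.** In sections 3.5.2 and 3.5.3, state that both tasks are done in the same prandial state for every participant. This means one fixed window, relative either to a standard study meal or to the overnight fast. The investigators should choose it: a fed window resembles ordinary eating, while a fasted one matches the state in which D2BP is measured. Use the same window at the one-year visit.

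Give the existing 3.5.1 hunger scale immediately before each task and record the time since last intake. In section 4, state that the task–D2BP association will be reported unadjusted, with a hunger-adjusted version as a sensitivity analysis. Go/No-Go may share the window for convenience.

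The cost is a scheduling line for the inpatient unit, one short scale per task and slightly less freedom in fitting tasks around scans. No new instrument is needed.
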